12. BIOMARKER ANALYSIS

Exploratory biomarker measurements will be made using appropriately validated assays. Results, if generated, will typically be expressed as % change from baseline and reported in a separate report.

13. PHARMACOGENOMIC ANALYSIS

Pharmacogenomic analysis will be conducted to correlate clinical observations (pharmacokinetics, safety, efficacy, or other effects) with genotypes observed in the study. Pharmacogenomic analysis may be conducted at a later time and will be reported in a separate report.

14. IMMUNOGENICITY ANALYSIS

Summary of immunogenicity results will be provided, and the incidence of immunogenicity will be calculated. The impact of immunogenicity on the pharmacokinetic profile, drug efficacy, and clinical safety will be evaluated if data allowed. This analysis will be reported separately

15. PLANNED INTERIM ANALYSIS

An interim analysis is planned when the last patient has completed the double-blind period. Final database lock will occur following the end of the open-label period.

The inferential analysis of efficacy variables for comparison between each fremanezumab treatment group (monthly dose and quarterly dose) and placebo will be done at the time of the first interim lock. The appropriate method for type 1 error control will be applied to the first interim analysis.

Efficacy analysis for the open-label portion of this study is considered exploratory and mainly descriptive. This analysis will be done at the time of the final database lock.

16. STATISTICAL SOFTWARE

All data listings, summaries, and statistical analyses will be generated using SAS[®] version 9.4 or later.

17. CHANGES TO ANALYSES SPECIFIED IN THE STUDY PROTOCOL

The planned interim analyses (see Section 2.5.1) have been updated to indicate that there will be 2 interim database locks and a final database lock. This was updated as clarification.

The PP analysis set definition (see Section 3.4) has been modified to update “completing the study” to “completing the double-blind treatment period”. This change has been made as this analysis set is only used for the primary and secondary efficacy endpoints which are for the double-blind treatment period only. Additional details have also been added regarding compliance and incorrect study drug administered. A statement has also been added to clarify that a blinded data review meeting will be conducted prior to the interim database lock to determine the exclusion of the patients.

APPENDIX A. E-DIARY QUESTIONNAIRE

The following questions are referring to yesterday (00:00 - 23:59)	
A1	Did you experience a headache of any severity yesterday?
A2	Did you have at least four (4) consecutive hours of headache yesterday?
A3	Did you have at least two (2) consecutive hours of headache yesterday?
A4	What was the greatest severity that your headache reached yesterday at any time?
A5	How many total hours did you have a headache(s) of any severity yesterday?
A6	How many total hours did you have a headache(s) of moderate or severe intensity yesterday?

The following questions are referring to yesterday (00:00 - 23:59) AT THE TIME WHEN YOUR HEADCAHE REACHED THE WORST SEVERITY	
B1	Was it worse on one side of the head than on the other, and/or limited to one side of the head?
B2	Was it pounding, pulsating, or throbbing?
B3	Was it made worse by routine activities such as walking or climbing stairs?
B4	Did you have nausea, or get sick to your stomach?
B5	Did light bother you more than when you didn't have a headache (did you experience photophobia)?
B6	Did sounds bother you more than when you didn't have a headache (did you experience phonophobia)?
The following questions are referring to yesterday (00:00 - 23:59)	
B7	Did you experience something like seeing spots, stars, lines, flashing lights, zigzag lines, or "heat waves" around the time of your headache? (This is different from "light bothers you")
B8	Did you have feelings such as numbness or tingling in any part of your body or face around the time of your headache?
B9	Did you experience something like seeing spots, stars, lines, flashing lights, zigzag lines, or "heat waves" similar to those you may have seen when you have a headache? (This is different from "light bothers you")
B10	Did you have feelings such as numbness or tingling in any part of your body or face, similar to what you may have felt when you have a headache?
C0	Did you take any medications yesterday for your headache/migraine?
C1	Were any of the following Medications taken yesterday?
	Local list of Triptans, Ergots and Opioid combinations, Presented in groups of 5 per screen, with Yes / No option to answer.

For the following questions please do not consider any medications you listed in the above questions.	
D1	Did you use any other prescription medications (i.e., opioids) in an effort to get relief from your headache/migraine?
D5	Did you use any other over the counter medications in an effort to get relief from your headache/migraine?
E1	Did you have problems falling sleep last night?
E2	Which of the following situations best describe your work/school performance yesterday, when you did not have a headache?
E3	What would better describe in general, how did you feel yesterday?
E4	How much of the time yesterday did you find it difficult to concentrate on what you needed to do?
E5	On average, how much of the time yesterday were you very tired, asleep, or feeling drained?
E6	Which of the following situations best describe your ability to perform household chores yesterday, when you did not have a headache?
E7	How engaged were you with your partner's or children's activities yesterday, when you didn't have a headache?
E8	Overall, how interested were you in doing daily activities yesterday?

APPENDIX B. LOGICS FOR ENDPOINTS DERIVATION

Migraine day: 1 of the following 5 options Primary endpoint			
OPTION 1			
Part 1	1	A1	YES
	2	A2	YES
		AND	
		TWO OF THE FOLLOWING	
Part 2	1	A4	Mod-S
	2	B1	YES
	3	B2	YES
	4	B3	YES
		AND	
		ONE OF THE FOLLOWING	
Part 3	1	B4	YES
	2	B5	YES
		AND	
	B6	YES	
OPTION 2			
1	A1	YES	
2	C0	YES	
3	C1	YES	
4	C1	ERGOT OR TRIPTAN	
OPTION 3			
1	A1	YES	
2	C0	YES	
3	D1	YES	
4	D1	ERGOT OR TRIPTAN	
OPTION 4			
1	A1	YES	
		AND	
		ONE OF THE FOLLOWING	
1	B7	YES	
		OR	
2	B8	YES	
OPTION 5: PROBABLE MIGRAINE			

If **Part 1** and **Part 2** met from option 1, **Part 3** needs ONLY one of the following:

Part 3		B5	YES
		B6	YES

If **Part 1** and **Part 3** met from option 1, **Part 2** needs ONLY one of the following:

[figure not shown]
Part 2	1	A4	Mod-S
	2	B1	YES
	3	B2	YES
	4	B3	YES

If **Part 2** and **Part 3** met from option 1, **Part 1** needs ONLY the following:

[figure not shown]
Part 1	1	A1	YES
---------------	---	----	-----

Headache day of at least moderate severity: 1 of the following 3 options		
OPTION 1		
1	A1	YES
2	A2	YES
3	A4	Moderate or Severe
OPTION 2		
1	A1	YES
2	C0	YES
3	C1	YES
4	C1	ERGOT OR TRIPTAN
OPTION 3		
1	A1	YES
2	C0	YES
3	D1	YES
4	D1	ERGOT OR TRIPTAN

[figure not shown]

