APPENDIX U. ICHD-3 DIAGNOSTIC CRITERIA

For further details, refer to [IHS 2013](#).

Migraine without Aura

- a. at least 5 attacks fulfilling criteria B through D
- b. headache attacks lasting 4 to 72 hours (untreated or unsuccessfully treated)
- c. headache has at least 2 of the following 4 characteristics:
 - unilateral location
 - pulsating quality
 - moderate or severe pain intensity
 - aggravation by, or causing avoidance of, routine physical activity (eg, walking or climbing stairs)
- d. during headache, at least 1 of the following:
 - nausea and/or vomiting
 - photophobia and phonophobia
- e. e. not better accounted for by another ICHD-3 diagnosis

Migraine with Aura

- a. at least 2 attacks fulfilling criteria B and C
- b. 1 or more of the following fully reversible aura symptoms:
 - visual
 - sensory
 - speech and/or language
 - motor
 - brainstem
 - retinal
- c. at least 2 of the following 4 characteristics:
 - at least 1 aura symptom spreads gradually over ≥ 5 minutes, and/or 2 or more symptoms occur in succession
 - each individual aura symptom lasts 5 to 60 minutes
 - at least 1 aura symptom is unilateral
 - the aura is accompanied, or followed within 60 minutes, by headache
- d. not better accounted for by another ICHD-3 diagnosis, and transient ischemic attack has been excluded

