This Statistical Analysis Plan (SAP) describes the planned analysis and reporting for Teva Branded Pharmaceutical Products Research and Development (R&D), Inc. study TV48125-CNS-30068, (A Multicenter, Randomized, Double-Blind, Parallel-Group, Placebo-Controlled Study with an Open-Label Period to Evaluate the Efficacy and Safety of Fremanezumab for the Prophylactic Treatment of Migraine in Patients with Inadequate Response to Prior Preventive Treatments), and was written in accordance with standard operating procedure (SOP) GBP_RD_702 (Statistical Analysis Plan).

The reader of this SAP is encouraged to read the study protocol for details on the conduct of this study, the operational aspects of clinical assessments, and the timing for completing the participation of a patient in this study.

The SAP is intended to be in agreement with the protocol, especially with regards to the primary and all secondary endpoints and their respective analyses. However, the SAP may contain more details regarding these particular points of interest, or other types of analyses (e.g. other endpoints). When differences exist in descriptions or explanations provided in the study protocol and this SAP, the SAP prevails; the differences will be explained in the clinical study report (CSR).

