6. EFFICACY ANALYSIS

6.1. General

The efficacy data for this study consist of headache related question responses (e.g., occurrence of headache, duration of headache in each day, maximum severity of headache, and acute migraine - specific medication use) collected daily using an electronic headache diary device.

In addition, the following questionnaires will be used for the assessments of migraine impairment, quality of life, and satisfaction of treatment etc. during the study.

- migraine-related disability using the HIT-6 (see [Appendix C](#))
- migraine-related disability using the MIDAS (see [Appendix D](#))
- migraine-specific quality of life, as measured by the MSQOL questionnaire (see [Appendix E](#))
- health status, as measured by the EQ-5D-5L questionnaire (see [Appendix G](#))
- patient depression status, as measured by the PHQ-2 and the PHQ-9 (see [Appendix H](#))
- patient work productivity and activity impairment, as measured by the WPAI questionnaire (see [Appendix I](#))
- assessment of patient satisfaction, as measured by the PGIC scale (see [Appendix J](#))

For the purpose of this study, a migraine day is endorsed when at least one of the following occurs:

- a calendar day (0:00 to 23:59) demonstrating at least 4 consecutive hours of a headache, meeting criteria for migraine with or without aura (Appendix U in protocol)
- a calendar day (0:00 to 23:59) demonstrating least 4 consecutive hours of a headache meeting criteria for probable migraine, a migraine subtype where only 1 migraine criterion is missing (Appendix U in protocol)
- a calendar day (0:00 to 23:59) demonstrating a headache of any duration that was treated with migraine- specific acute medications (triptans and ergot compounds)

A headache day of at least moderate severity is endorsed when at least 1 of the following situations occurs:

- a calendar day (0:00 to 23:59) demonstrating at least 4 consecutive hours of headache of at least moderate severity
- a calendar day (0:00 to 23:59) demonstrating a headache of any duration that was treated with migraine- specific acute medications (triptans and ergot compounds)

The derivation logic is presented in [Appendix B](#).

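### SAP Appendix B counts short headaches with aura symptoms as migraine days, against the 4-hour rule in SAP 6.1 and protocol 9.5

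*SAP*

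**What the plan says.** Protocol 9.5 and SAP 6.1 give the same three routes to a migraine day. The first is a calendar day "demonstrating at least 4 consecutive hours of a headache, meeting criteria for migraine with or without aura". The second is the same minimum duration for probable migraine. The third is a headache of any duration treated with a triptan or ergot. Only the third route waives the duration.

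SAP 6.1 then closes its definitions with "The derivation logic is presented in" Appendix B. That appendix labels the table as the primary endpoint and begins "Migraine day: 1 of the following 5 options". In terms of the diary items in SAP Appendix A:

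- Option 1 needs A1 (any headache) and A2 (4 consecutive hours), plus pain features and associated symptoms.
- Options 2 and 3 are the triptan or ergot routes.
- Option 4 needs A1 and either B7 (visual symptoms) or B8. Item B8 reads "Did you have feelings such as numbness or tingling in any part of your body or face around the time of your headache". A2 is not listed.
- Option 5 is probable migraine. Its third branch reads "If Part 2 and Part 3 met from option 1, Part 1 needs ONLY the following", and the only item shown is A1.

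The SAP Introduction has a precedence clause: "When differences exist in descriptions or explanations provided in the study protocol and this SAP, the SAP prevails". SAP Section 17 lists two changes from the protocol. One is the number of database locks; the other begins "The PP analysis set definition (see Section 3.4) has been modified". The migraine-day rule is not among them.

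**The concern.** A patient with a two-hour headache and tingling, who takes no triptan or ergot, has a migraine day under Appendix B and none under SAP 6.1 or the protocol. Two programmers who each follow the SAP faithfully could therefore produce different primary datasets.

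The migraine-day count feeds the baseline value (formula 3), the primary endpoint, the MMRM and multiple-imputation sensitivity analyses, the month-1 change, and the 50% responder endpoints at 12 weeks and at month 1. The 12-week responder endpoint is the first secondary in the testing order. If the conflict is still open when treatment codes are released, whichever rule is used could look as if it was chosen after seeing the results.

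**Working it through.** **Plan's own figure.** The plan gives no figure for this point. The sample size behind the endpoint (difference 1.8 days, SD 6, 90% power, alpha 0.05) does reproduce: 234 per group by the normal approximation and 234.5, rounded up to 235, by the t-test. Then 235/0.88 gives 268. The conflict does not alter that calculation.

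**Side by side, for a headache not treated with a triptan or ergot**

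| Route | SAP 6.1 and protocol 9.5 | SAP Appendix B |
|---|---|---|
| Migraine without aura | 4 hours | A1 and A2 (Option 1) |
| Migraine with aura | 4 hours | A1 only (Option 4) |
| Probable migraine, first two branches | 4 hours | A1 and A2 (Option 5) |
| Probable migraine, third branch | 4 hours | A1 only, as printed (Option 5) |

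Option 4 looks intact in the text available. The appendix does apply the 4-hour item elsewhere: in Option 1, and in the non-triptan route to a headache day of at least moderate severity. A figure is missing beside the third branch of Option 5, so a lost row there cannot be excluded. The finding rests on Option 4 without it.

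**Logical scope.** Fix A1=YES, A2=NO and no triptan or ergot. The remaining items are A4 (moderate or severe, or not) and B1 to B8, which gives 2^9 = 512 answer patterns.

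- Text definition: 0 count.
- Option 4 (B7 or B8 positive): 512 × 3/4 = 384.
- Third branch of Option 5 with B7 and B8 both negative: at least two of A4, B1, B2, B3 gives 11 combinations; B4, or both B5 and B6, gives 5 combinations; 11 × 5 = 55.
- Total if that branch stands as printed: 384 + 55 = 439.

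Across all 2^11 = 2,048 patterns with A1=YES (A2 and triptan or ergot use now free), Appendix B counts 1,944 and the text 1,505. The difference is the same 439, and no pattern counts under the text alone. Adding A2 to Option 4 only leaves 55 × 4 = 220 mismatches; adding it in both places leaves 0. These counts take B7 or B8 as the aura criterion on both sides. They are patterns, not expected frequencies of days.

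**Responder status, invented examples.** Formula (4) of SAP 6.1 is (baseline − postbaseline)/baseline.

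| Example | By text | By Appendix B |
|---|---|---|
| (a) 10 to 5 text days, plus 2 short aura days in both periods | (10 − 5)/10 = 50.0%, responder | (12 − 7)/12 = 41.7%, non-responder |
| (b) 10 to 6 text days, with short aura days falling from 4 to 0 | (10 − 6)/10 = 40.0%, non-responder | (14 − 6)/14 = 57.1%, responder |

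In (a) the change is −5 days under both rules. In (b) it is −4 by the text and −8 by Appendix B. Responder status can therefore move in either direction.

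**Which side was intended.** The documents do not settle this. Protocol Appendix U gives a duration for migraine without aura, "headache attacks lasting 4 to 72 hours (untreated or unsuccessfully treated", and no headache duration for migraine with aura. That could explain Option 4. Inclusion criterion g has no 4-hour rule for aura, but it has none for migraine without aura either, so it is weak evidence of an aura-specific exemption.

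**The case against.** The best reply is that the ambiguity is smaller than it looks. SAP 6.1 itself hands the derivation to Appendix B, which is the only item-level algorithm, so a programmer has one rule to code and the prose merely fails to match it. That rule applies to run-in and treatment days in every arm, so by itself it neither biases the comparison nor inflates type I error. The SAP is to be approved before the first interim lock and unblinding. Its Introduction promises that differences from the protocol will be explained in the study report, and protocol 9.15 allows several places to describe deviations. The pattern counts say nothing about how often such days occur, and the responder examples are invented.

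Much of this stands. There is no evidence of bias, the size is unknown, and the counts show scope only. It does not remove the defect. SAP 6.1 states the 4-hour rule itself, so the conflict lies inside the SAP, where the precedence clause does not reach. An explanation in the study report comes after unblinding.

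A further objection is fair: adding A2 does not make Option 4 match the protocol completely. Appendix U asks for at least two of four aura characteristics, while Option 4 accepts one symptom. That belongs in the same edit.

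**Conclusion.** The concern holds. SAP Appendix B derives the primary-endpoint migraine day by a rule that differs from SAP 6.1 and protocol 9.5, and the difference is not declared. It must be resolved before the first interim lock because it concerns what the primary endpoint counts, however large the effect proves to be. The conflict is certain for Option 4. For the third branch of Option 5 it depends on the table being complete as printed. The size and direction of the effect on the treatment difference cannot be derived from the documents.

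**What to change.** Before the first interim lock and unblinding, make SAP 6.1 and Appendix B state one migraine-day definition.

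- **Default, in line with the protocol:** add A2=YES to Option 4. Check the source page for the third branch of Option 5; if A2 is absent there, add it. Parts 1 to 3 are then all met, so the branch duplicates Option 1 and can be deleted.
- **If Appendix B was intended:** amend SAP 6.1 to match it and list the change from protocol 9.5, with the reason, in Section 17.
- **In either case:** say whether one positive answer to B7 or B8 is the working aura criterion. The items in SAP Appendix A do not ask about the spread, duration or side of aura symptoms, so the two-of-four rule in Appendix U cannot be fully applied from the diary.

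A prespecified sensitivity analysis of the primary endpoint under the other definition would show how much the choice matters. It is useful, but the correction does not depend on it.

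The cost is SAP wording and a small programming change. The diary already collects A2, so no new data are needed and the sample size is unchanged.

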APPENDIX C. HIT-6™ HEADACHE IMPACT TEST

[figure not shown]

[figure not shown]
APPENDIX D. THE MIGRAINE DISABILITY ASSESSMENT

[figure not shown]

[figure not shown]
**APPENDIX E. MIGRAINE-SPECIFIC QUALITY OF LIFE
QUESTIONNAIRE (MSQ) (VERSION 2.1)**

[figure not shown]

[figure not shown]

[figure not shown]

[figure not shown]
APPENDIX F. SCORING INSTRUCTIONS FOR MSQOL (VERSION 2.1)

[figure not shown]

[figure not shown]
APPENDIX G. EQ-5D-5L AND EQ VAS

[figure not shown]

[figure not shown]

[figure not shown]
**APPENDIX H. PATIENT HEALTH QUESTIONNAIRE (PHQ-2) AND
(PHQ-9)**

**APPENDIX I. WORK PRODUCTIVITY AND ACTIVITY IMPAIRMENT
QUESTIONNAIRE: GENERAL HEALTH V2.0 (WPAI:GH)**

**APPENDIX J. PATIENT’S GLOBAL IMPRESSION OF CHANGE (PGIC)
SCALE**
